3.2 Exploratory objectives

Exploratory objective 1:

Mapping of FP-specific serum neutralizing activity

Exploratory objective 2:

To evaluate the ability of the vaccine regimen to elicit early FP broad neutralizing antibody memory B-cell lineages.

Exploratory objective 3:

To evaluate the humoral and cellular immune response to vaccination regimens including FP-conjugate vaccine and Trimer 4571 to compare responses between the regimens.

Exploratory objective 4:

To conduct analyses related to furthering the understanding of HIV, immunology, vaccines, and clinical trial conduct. To further evaluate immunogenicity of each vaccine regimen, additional immunogenicity assays may be performed in a subset of participants, including on samples from other timepoints, based on the HVTN Laboratory Assay Algorithm.

4 Laboratory strategy

The laboratory strategy for this protocol will focus on interrogations of the humoral and cellular immune response as it relates to the ability of FP-conjugate and Trimer 4571 vaccines to elicit FP-specific binding antibodies. ~~the elicitation of broadly neutralizing antibodies. Magnitude, breadth, kinetics and durability of serum neutralizing antibodies will be assessed by using vaccine-matched and non-matched (heterologous) tier 2 HIV-1 Env pseudotyped viruses in the TZM-bl assay. Serum antibodies will be further interrogated by measuring IgG binding to the vaccine antigens and a specialized set of epitope-domain-specific antigens. A role for T cell help will be investigated by assessing antigen-specific CD4+ T cells by intracellular cytokine staining as measured by flow cytometry. To gain further insights into the requirements for broadly neutralizing antibody induction, exploratory studies may be conducted to assess antigen-specific B-cell frequencies and to interrogate B-cell lineages that give rise to FP-specific antibodies in vaccine recipients. Serum neutralizing antibodies may also be assessed in the TZM-bl assay. The detailed laboratory strategy and the technical details are described in the Central Assay Plan and will be updated as new reagents and techniques are incorporated into assay planning. This document will be available on the protocol webpage. Descriptions of the standard HVTN laboratory assays can be found online at~~
<https://www.hvtn.org/content/dam/hvtn/scientific-programs/hvtn-laboratory-assay-descriptions.pdf>

5 Study design

This is an open-label, dose-escalation study to examine the safety, tolerability, and immunogenicity dose of adjuvanted Fusion Peptide Vaccine alone or in prime-boost regimens with adjuvanted Trimer 4571 and Trimer 6934 vaccines in healthy adults. The hypothesis is that the vaccines will be safe, tolerable for human administration and will induce detectable immune response.

5.1 Study population

All inclusion and exclusion criteria must be met for eligibility. Screening procedures to determine eligibility must be performed within 56 days prior to enrollment.

Investigators should always use good clinical judgment in considering a volunteer's overall fitness for trial participation. Some volunteers may not be appropriate for enrollment even if they meet all inclusion/exclusion criteria. Medical, psychiatric, occupational, or other conditions may make evaluation of safety and/or immunogenicity difficult, and some volunteers may be poor candidates for retention.

5.1.1 Inclusion criteria

1. Able and willing to complete the informed consent process, including an Assessment of Understanding (AoU): volunteer demonstrates understanding of this study, completes a questionnaire prior to first vaccination with verbal demonstration of understanding of all questionnaire items answered incorrectly.
2. 18-50 years old, inclusive, on day of enrollment.
3. Agrees to comply with planned study procedures and be available for clinic follow-up through the last clinic visit.
4. Agrees not to enroll in another study of an investigational agent during participation in the trial, including severe acute respiratory syndrome coronavirus 2 (SARS-CoV-2) investigational agents that may subsequently obtain emergency use authorization (EUA) or undergo licensure by the FDA. If a potential participant is already enrolled in a SARS-CoV-2 clinical trial, prior approvals from the SARS-CoV-2 study sponsor and HVTN 303 PSRT are required prior to enrollment in HVTN 303.
5. In good general health without clinically significant medical history.
6. Physical examination and laboratory results without clinically significant findings that would interfere with assessment of safety or reactogenicity.

7. Body Mass Index (BMI) ≤ 40 .
8. Assessed as low risk for HIV acquisition as per [Appendix K](#), agrees to discuss HIV infection risks, agrees to risk reduction counseling, and agrees to avoid behavior associated with high risk of HIV exposure through the final study visit. Low risk may include persons stably taking pre-exposure prophylaxis (PrEP) as prescribed for 6 months or longer (see [Appendix K](#) for protocol safety review team [PSRT]) consultation requirements).
9. Suitable injection sites in the deltoid muscle of each arm, as assessed by a clinician.

Laboratory Criteria within 56 days prior to enrollment:

10. White blood cells (WBCs) 2,500-12,000/mm³
11. WBC differential either within institutional normal range or approved by the Investigator of Record (IoR) as “not clinically significant.”
12. Platelets = 125,000 – 500,000/mm³
13. Hemoglobin
 - ≥ 11.0 g/dL for volunteers who were assigned female sex at birth
 - ≥ 13.0 g/dL for volunteers who were assigned male sex at birth and transgender males who have been on hormone therapy for more than 6 consecutive months
 - ≥ 12.0 g/dL for transgender females who have been on hormone therapy for more than 6 consecutive months
 - For transgender participants who have been on hormone therapy for less than 6 consecutive months, determine hemoglobin eligibility based on the sex assigned at birth
14. Serum creatinine $\leq 1.1 \times$ upper limit of normal (ULN) based on the institutional normal range.
15. Alanine aminotransferase (ALT) $\leq 1.25 \times$ ULN based on the institutional normal range.
16. Negative for HIV infection by an (US) Food and Drug Administration (FDA)-approved enzyme immunoassay (EIA) or chemiluminescent microparticle immunoassay (CMIA).

17. Negative for anti-Hepatitis C antibodies (anti-HCV) or negative HCV nucleic acid test (NAT) if anti-HCV antibodies are detected.
18. Negative for Hepatitis B surface antigen.

For a volunteer capable of becoming pregnant:

19. Agrees to use effective means of birth control from at least 21 days prior to enrollment through 12 weeks after the last product administration.
20. Negative β -HCG (beta human chorionic gonadotropin) pregnancy test (urine or serum) at screening and prior to each study product administration on the day of study product administration.

5.1.2 Exclusion criteria

1. Active duty and reserve US military personnel

For a volunteer capable of becoming pregnant:

2. Breast-feeding or planning to become pregnant from at least 21 days prior to enrollment through 12 weeks after the last product administration.

Participant has received any of the following:

3. An investigational HIV vaccine (previous placebo recipients are not excluded).
4. Immunosuppressive medications received within 168 days before first vaccination (Not exclusionary: [1] corticosteroid nasal spray; [2] inhaled corticosteroids; [3] topical corticosteroids for mild, uncomplicated dermatologic condition; or [4] a single course of oral/parenteral prednisone or equivalent at doses ≤ 60 mg/day and length of therapy < 11 days with completion at least 30 days prior to enrollment).
5. Blood products within 60 days prior to enrollment
6. Monoclonal antibodies (mAbs), whether licensed or investigational. Exceptions may be made by the HVTN 303 PSRT on a case-by-case basis
7. Receipt of any of the following:
 - Within 4 weeks prior to enrollment:
 - Any licensed live, attenuated vaccine (except for the Jynneos monkeypox vaccine)
 - Any adenoviral-vectorized SARS-CoV-2 vaccine with FDA Emergency Use Authorization (EUA), FDA licensure or World Health Organization (WHO) Emergency Use Listing (EUL)

- ACAM2000 vaccine for Monkeypox
- ACAM2000 received greater than 4 weeks prior to enrollment but vaccination scab is still present
- Within 2 weeks prior to enrollment:
 - Any licensed killed/subunit/inactivated vaccine
 - Any mRNA based or protein SARS-CoV-2 vaccines with FDA EUA, FDA licensure, or WHO EUL
 - Jynneos Monkeypox vaccine for Monkeypox

Receipt of any SARS-CoV-2 vaccination series should be completed 4 weeks prior to enrollment when possible.

8. Investigational research agents with a half-life of 7 or fewer days within 4 weeks prior to enrollment. If a potential participant has received investigational agents with a half-life greater than 7 days (or unknown half-life) within the past year, PSRT approval is required for enrollment.
9. Current allergen immunotherapy with antigen injections, unless on maintenance schedule.
10. Current anti-TB prophylaxis or therapy.

Participant has any of the following:

11. Serious adverse reactions to vaccines or vaccine components.
12. Hereditary angioedema, acquired angioedema, or idiopathic forms of angioedema.
13. Hypertension that is not well controlled.

- If a person has been found to have elevated blood pressure or hypertension during screening or previously, exclude for blood pressure that is not well controlled. Well-controlled blood pressure is defined in this protocol as consistently < 140 mm Hg systolic and < 90 mm Hg diastolic, with or without medication, with only isolated, brief instances of higher readings, which must be ≤ 150 mm Hg systolic and ≤ 100 mm Hg diastolic. For these volunteers, blood pressure must be < 140 mm Hg systolic and < 90 mm Hg diastolic at enrollment.
- If a person has NOT been found to have elevated blood pressure or hypertension during screening or previously, exclude for systolic blood pressure ≥ 150 mm Hg at enrollment or diastolic blood pressure ≥ 100 mm Hg at enrollment.

14. Asthma is excluded if the participant has ANY of the following:
 - Required either oral or parenteral corticosteroids for an exacerbation two or more times within the past year; OR
 - Needed emergency care, urgent care, hospitalization, or intubation for an acute asthma exacerbation within the past year (eg, would NOT exclude individuals with asthma who meet all other criteria but sought urgent/emergent care solely for asthma medication refills or co-existing conditions unrelated to asthma); OR
 - Uses a short-acting rescue inhaler more than 2 days/week for acute asthma symptoms (ie, not for preventive treatment prior to athletic activity); OR
 - Uses medium-to-high-dose inhaled corticosteroids (greater than 250 mcg fluticasone or therapeutic equivalent per day), whether in single-therapy or dual-therapy inhalers (ie, with a long-acting beta agonist [LABA]); OR
 - Uses more than one medication for maintenance therapy daily. Inclusion of anyone on a stable dose of more than one medication for maintenance therapy daily for greater than two years requires PSRT approval.
15. Autoimmune disease, current or history, including psoriasis.
16. Clinically significant immunodeficiency.
17. AESIs: Volunteers who currently have, or have a history of, any condition that could be considered an AESI for the product(s) administered in this protocol (representative examples are listed in [Appendix M](#))
18. History of generalized urticaria, angioedema, or anaphylaxis. (Not exclusionary: angioedema or anaphylaxis to a known trigger with at least 5 years since last reaction to demonstrate satisfactory avoidance of trigger.).
19. Diabetes mellitus type 1 or type 2.
20. Bleeding disorder diagnosed by a doctor (eg, factor deficiency, coagulopathy, or platelet disorder requiring special precautions) or significant bruising or bleeding difficulties with IM injections or blood draws.
21. Seizure disorder other than: 1) febrile seizures, 2) seizures secondary to alcohol withdrawal more than 3 years ago, or 3) seizures that have not required treatment within the last 3 years.
22. Asplenia or functional asplenia.

23. Malignancy (Not excluded from participation: Volunteer who has had malignancy excised surgically and who, in the investigator's estimation, has a reasonable assurance of sustained cure, or who is unlikely to experience recurrence of malignancy during the period of the study).
24. Any other chronic or clinically significant condition that in the clinical judgement of the investigator would jeopardize the safety or rights of the study participant, including, but not limited to: clinically significant forms of drug or alcohol abuse, serious psychiatric disorders, or cancer that, in the clinical judgement of the site investigator, has a potential for recurrence (excluding basal cell carcinoma).

5.1.3 Leukapheresis Eligibility Criteria

Only participants who received two vaccinations in Part B (Groups 7-8) and who consent to leukapheresis will undergo leukapheresis at 10 months +/- 2 months post–last vaccination in order to collect blood cells for research.

~~Part B (groups 6-8) participants who consent to leukapheresis (see Section 2.7) will be asked to undergo leukapheresis at 2 weeks post last vaccination in order to collect blood cells of special interest for research.~~ These participants must meet all of the following criteria:

1. Weight \geq 110 pounds
2. Meeting local site requirements related to these procedures (eg, any specific hemoglobin level requirements by pheresis center)
3. Negative beta-human chorionic gonadotropin (β -HCG) pregnancy test (urine or serum) performed by a study clinician within 72 hours prior to the apheresis procedure

5.2 Participant departure from vaccination schedule or withdrawal

On January 13, 2023, a protocol memo was distributed informing the clinical research sites that all vaccinations in HVTN 303 were permanently discontinued. Hence, the language that are no longer relevant for this amendment is marked with strikethrough.

5.2.1 Delaying vaccinations for a participant

~~Under certain circumstances, a participant's scheduled vaccination will be delayed. The factors to be considered in such a decision include but are not limited to the following:~~

- ~~Intercurrent illness or pre vaccination abnormal vital signs or clinical symptoms that may mask assessment of vaccine reaction~~
- ~~Treatment with systemic glucocorticoids (eg, prednisone or other glucocorticoid), with the exception that study injection may continue per principal investigator (PI) discretion if the next study injection occurs at least 2 weeks following completion of glucocorticoid treatment~~
- ~~Receipt of any live attenuated vaccines within 4 weeks prior to study vaccine administration~~
- ~~Receipt of any inactivated vaccines within 2 weeks prior to study vaccine administration with exceptions as below:~~
- ~~Timing of study vaccination with respect to SARS CoV 2 vaccination: if the SARS CoV 2 vaccination series was not completed prior to enrollment, attempt to time SARS CoV 2 vaccination no closer than 2 weeks (for protein vaccines and mRNA based vaccines) or 4 weeks (for adenoviral vectored) before or after study vaccination.~~
- ~~Timing of study vaccination with respect to Monkeypox vaccination: attempt to separate study vaccination from administration of Monkeypox vaccine prior to study enrollment, or during study based on the instruction below:~~
 - ~~Jynneos vaccine:~~
 - ~~after administration of Jynneos vaccine, a minimum of 2 weeks is required before administration of study vaccine~~
 - ~~after study vaccine administration, a minimum of 2 weeks is required before administration of Jynneos vaccine~~
 - ~~ACAM2000 vaccine: (Note: in addition to the instructions mentioned below, sites should consult with HVTN 303 PSRT for any participants who may be scheduled to receive ACAM2000 vaccine after enrollment)~~
 - ~~after administration of ACAM2000 vaccine, a minimum of 4 weeks is required before administration of study vaccine; if vaccination scar is not present~~
 - ~~if ACAM2000 vaccine is received greater than 4 weeks prior to enrollment but vaccination scar is still present, delay study vaccination until the scar is no longer present~~
 - ~~after study vaccine administration, a minimum of 2 weeks is required before administration of ACAM2000 vaccine~~

~~Vaccinations should not be administered outside the visit window period specified in [Appendix E](#) and [Appendix F](#).~~

5.2.2 Discontinuation of study vaccine administration

~~Under certain circumstances, an individual participant's vaccinations will be permanently discontinued. Specific events that will result in stopping a participant's vaccination schedule include:~~

- ~~SAE that is subsequently considered to be related to vaccination~~
- ~~Pregnancy (regardless of outcome)~~
- ~~HIV infection~~
- ~~Grade 3 AE assessed as related to study vaccine, with the following exceptions:~~
 - ~~Grade 3 subjective reactogenicity and injection site reactions: injection site pain/tenderness and erythema/induration (grade 3 by size only), fatigue, generalized myalgia, generalized arthralgia, chills, headache, nausea (unless intravenous [IV] rehydration required)~~
 - ~~AEs reviewed by the PSRT and approved for vaccination continuation~~
- ~~Grade 4 AE assessed as related to study vaccine~~
- ~~Clinically significant type 1 hypersensitivity associated with study vaccine~~

~~For ease of reference and review, the clinically significant type 1 hypersensitivity definition, as per the Second National Institute of Allergy and Infectious Disease/Food Allergy and Anaphylaxis Network symposium criteria for anaphylaxis (28), is provided below:~~

~~Anaphylaxis is highly likely when any one of the following criteria are fulfilled:~~

1. ~~Acute onset of an illness (minutes to several hours) with involvement of the skin, mucosal tissue, or both (eg, generalized hives, pruritus or flushing, swollen lips/tongue/uvula)~~

~~AND AT LEAST ONE OF THE FOLLOWING:~~

- a. ~~Respiratory compromise (eg, dyspnea, wheeze, bronchospasm, stridor, reduced peak expiratory flow [PEF], hypoxemia)~~
- b. ~~Reduced blood pressure (BP) or associated symptoms of end-organ dysfunction (eg, hypotonia [collapse], syncope, incontinence)~~

2. ~~Two or more of the following that occur rapidly after exposure to a likely allergen for that patient [participant] (minutes to several hours):~~

- a. ~~Involvement of the skin-mucosal tissue (eg, generalized hives, itch-flush, swollen lips/tongue/uvula)~~
- b. ~~Respiratory compromise (eg, dyspnea, wheeze/bronchospasm, stridor, reduced PEF, hypoxemia)~~
- c. ~~Reduced BP or associated symptoms (eg, hypotonia [collapse], syncope, incontinence)~~
- d. ~~Persistent gastrointestinal symptoms (eg, crampy abdominal pain, vomiting)~~

3. ~~Reduced BP after exposure to known allergen for that patient [participant] (minutes to several hours). Adults: systolic BP of less than 90 mm Hg or greater than 30% decrease from that person's baseline~~

- ~~PI assessment that it is not in the best interest of the participant to continue receiving study vaccine~~
- ~~New diagnosis of or newly disclosed AESI (see [Appendix M](#) Appendix M)~~
- ~~Co-enrollment in a study with an investigational research agent (rare exceptions allowing for the continuation of vaccinations may be granted with the unanimous consent of the HVTN 303 PSRT)~~

~~Participants discontinuing study vaccine for reasons other than HIV infection should be encouraged to participate in follow-up visits and procedures per the protocol. At the discretion of the CRS clinician and the PSRT (for composition of PSRT see [Section 9.3](#)), some clinic procedures and sample collections may be modified or discontinued.~~

~~If a participant becomes HIV-infected during the course of the study, no additional study vaccine will be administered. participants will be encouraged to continue scheduled study visits for up to 12 months following their last study vaccine administration. At post infection follow-up visits, only samples for protocol-specified clinical labs (with the exception of HIV diagnostic testing) will be collected. In addition, some clinic procedures may be modified or discontinued.~~

5.2.3 Participant departure from vaccine schedule

~~If a participant misses a scheduled vaccination, they are eligible for future vaccinations.~~

5.2.4 Discontinuation of study participation

A participant may be discontinued from protocol participation for the following reasons:

- Participant voluntarily withdraws;
- CRS determines the participant is lost to follow-up;
- The investigational new drug (IND) application Sponsor or regulatory authorities stop the study; or
- PI assessment that it is not in the best interest of the participant to continue participation in the study or that the participant's compliance with the study is not sufficient.

If a participant terminates participation in the study early for any reason, the site principal investigator should consider if the following assessments are appropriate: end-of-study HIV test, complete blood count (CBC) with differential, serum chemistry, physical examination, and if indicated, a pregnancy test (see [Appendix A](#), [Appendix B](#), [Appendix C](#) and [Appendix D](#)). For participants with HIV infection, please see Section [8.7](#). If the site principal investigator has questions regarding a termination visit, they should consult with the PSRT.

6 Statistical considerations

On January 13, 2023, a protocol memo was distributed informing the clinical research sites that all vaccinations in HVTN 303 were permanently discontinued. The sample size calculations for safety and immunogenicity were updated based on the actual numbers of participants who were enrolled in the study and the updated objectives in Section 3. The language shown below is the revised version of the original protocol (v1.0) as per the sample size and the design of the current protocol version 2.0.

6.1 Accrual and sample size calculations

Recruitment will target 60 (up to 70) healthy adult participants 18 to 50 years of age. However, due to the early termination, the study enrolled a total of 44 participants (15 in Part A and 29 in Part B). The primary goal of this study is to identify safety concerns that may be associated with the study products.

Since enrollment is concurrent with receiving the first study vaccination, all enrolled participants will provide some safety data. For immunogenicity analyses, the sample calculations are based on the available samples.

6.2 Sample size calculations for safety

The goal of the safety evaluation for this study is to identify safety concerns associated with product administration. The ability of the study to detect SAEs (see Section 9.1) can be expressed by the true event rate above which at least 1 SAE would likely be observed and the true event rate below which no events would likely be observed. Specifically, for each vaccine arm of the study ($n = 3$) in Part A, there is a 90% chance of observing at least 1 event if the true rate of such an event is 53.6% or more; and there is a 90% chance of observing no events if the true rate is 1% or less. For a vaccine arm in Part B ($n = 9$ or 10), there is a 90% chance of observing at least 1 event if the true rate of such an event is 22.6% or 20.6% or more; and there is a 90% chance of observing no events if the true rate is 1% or less. For a combined vaccine arm (Groups 1-5 in Part A and Groups 6-8 in Part B) of the study ($n = 44$), there is a 90% chance of observing at least 1 event if the true rate of such an event is 5.1% or more; and there is a 90% chance of observing no events if the true rate is 0.2% or less. As a reference, in HVTN vaccine trials from April 2008 through March 2018, about 1.7% of participants who received placebos experienced an SAE.

Binomial probabilities of observing 0, 1 or more, and 2 or more events among arms of size 3, 9, 10, and 44 are presented in Table 6-1 for a range of possible true adverse event rates. These calculations provide a more complete picture of the

sensitivity of this study design to identify potential safety problems with the vaccine.

Table 6-1 Probability of observing 0 events, 1 or more events, and 2 or more events, among arms of size 3, 9, 10, and combined arms of size 44, for different true event rates

True event rate (%)	Pr(0/3)	Pr(1+/3)	Pr(2+/3)	Pr(0/10)	Pr(1+/10)	Pr(2+/10)	Pr(0/9)	Pr(1+/9)	Pr(2+/9)	Pr(0/44)	Pr(1+/44)	Pr(2+/44)
1	97	3	0	90.4	9.6	0.4	91.4	8.6	0.3	64.3	35.7	7.2
4	88.5	11.5	0.5	66.5	33.5	5.8	69.3	30.7	4.8	16.6	83.4	53
5	85.7	14.3	0.7	59.9	40.1	8.6	63	37	7.1	10.5	89.5	65.3
10	72.9	27.1	2.8	34.9	65.1	26.4	38.7	61.3	22.5	1	99	94.3
20	51.2	48.8	10.4	10.7	89.3	62.4	13.4	86.6	56.4	<0.1	>99.9	99.9
30	34.3	65.7	21.6	2.8	97.2	85.1	4	96	80.4	<0.1	>99.9	>99.9
40	21.6	78.4	35.2	0.6	99.4	95.4	1	99	92.9	<0.1	>99.9	>99.9
50	12.5	87.5	50	0.1	99.9	98.9	0.2	99.8	98	<0.1	>99.9	>99.9
60	6.4	93.6	64.8	0	>99.9	99.8	0	>99.9	99.6	<0.1	>99.9	>99.9

An alternative way of describing the statistical properties of the study design is in terms of the 95% confidence interval (CI) for the true rate of an adverse event based on the observed data. [Table 6-2](#) shows the 2-sided 95% confidence intervals for the probability of an event based on a particular observed rate. Calculations are done using the score test method (52). If none of the participants in a group of size of 3 (eg, Groups 1-5 in Part A) or in a group of size of 9 or 10 (eg, the Groups 6-8 in Part B) are experiencing a safety event, the 95% 2-sided upper confidence bound for the true rate of such events in the total vaccinated population is 56.1% or 29.9% or 29.2%, respectively. For the combined vaccine arms in Part A and Part B (Groups 1-8, n = 44), the 95% 2-sided upper confidence bound for this rate is 9.8%.

Table 6-2 Two-sided 95% confidence intervals based on observing a particular rate of safety endpoints for arms of size 3, 9, 10 or combined arms of size 44

Observed event rate	95% Confidence interval (%)
0/3	[0, 56.1]
1/3	[6.1, 79.2]
2/3	[20.8, 93.9]
0/9	[0, 29.9]
1/9	[2, 43.5]
2/9	[6.3, 54.7]
0/10	[0, 29.2]
1/10	[0.1, 30.5]
2/10	[0.2, 31.9]
0/44	[0.1, 9.8]
1/44	[0.3, 11.4]
2/44	[0.6, 12.9]

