* In Part A, up to 20 participants may be enrolled if needed for safety evaluations. Additional participants may be enrolled to ensure the availability of 2-week safety data from at least 3 participants per group. Refer to the HVTN 303 Study Specific Procedures (SSP) for further details.

§ In Part B, up to 50 participants may be enrolled if needed for safety evaluations. Additional participants may be enrolled to ensure the availability of 2-week safety data from at least 15 participants per group. Refer to the HVTN 303 SSP for further details.

† Total up to 70 participants can be enrolled if needed for safety evaluations. Refer to the HVTN 303 SSP for further details.

Notes:

***Vaccination in Part B starting from Week 8 onwards did not take place.

Actual Ns for Group 6, 7 and 8 were 10, 10 and 9 respectively. In Part B total 29 participants were enrolled.

Part A of the study may begin with direct enrollment of participants into the following groups simultaneously:

- Group 1 with no more than 1 participant enrolled per day for the 3 participants.
- Group 3 with no more than 1 participant enrolled per day for the 3 participants.

After Groups 1 and 3 have been fully enrolled, the study will be placed on a safety hold. No additional enrollments will proceed until the Protocol Safety Review Team (PSRT) has determined it is safe to do so. Once all of the reactogenicity and 2-week safety data from at least 6 participants have been submitted to the database, the PSRT must assess the accumulated product-specific data as showing no significant safety concerns before proceeding with enrollment of Groups 2, 4 and 5. If the PSRT has determined it is safe to proceed after reviewing data from Groups 1 and 3, the following groups may begin simultaneously:

- Group 2 with no more than 1 participant enrolled per day for the 3 participants
- Group 4 with no more than 1 participant enrolled per day for the 3 participants
- Group 5 with no more than 1 participant enrolled per day for the 3 participants

Once Groups 2, 4 and 5 have been fully enrolled, the study will be placed on a safety hold before proceeding with Part B. Once all of the reactogenicity and 2-week safety data from at least 9 participants have been submitted to the database, the PSRT must assess the accumulated product-specific data as showing no significant safety concerns before proceeding with enrollment of Part B.

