6.2.1 Sample size calculations for immunogenicity

The main goals of this trial regarding immunogenicity outcomes involve assessing the ability of FP-conjugate and Trimer 4571 vaccines alone or co-administration to elicit antibody binding FP and envelop trimer antigens and mapping FP-specific serum neutralizing activity induced by the prime vaccines regimens in Groups 5-8 and prime boost vaccines regimens in Groups 7-8. No adjustment for multiple comparisons will be made for the use of multiple assays. The precision with which the true response rate can be estimated from the observed data depends on the true underlying response rate and the sample size. Two-sided 95% CIs for the response rate based on observing a particular rate of responses in the vaccinees is shown in [Table 6-3](#). Calculations are done using the score test method (52). The sample size of n = 13 (Groups 5-6) and n=9 for each of Groups 7 and 8 will be used to evaluate the immunogenicity post the 1st vaccination induced by the vaccination; the sample sizes of n=4, 5 for Groups 7-8 will be used to evaluate the immunogenicity post the 2nd vaccination.

Table 6-3 Two-sided 95% confidence intervals for the true response rate based on observing a particular rate of responses in the vaccinees (n =4, 5, 9, 13)

No. of responses	Observed response rate (%)	95% Confidence interval
2/4	50	[15, 85]
4/4	100	[51, 100]
2/5	40	[11.8, 76.9]
4/5	80	[37.6, 96.4]
3/9	33.3	[12.1, 64.6]
6/9	66.7	[35.4, 87.9]
9/9	100	[70.1, 100]
3/13	23.1	[8.2, 50.3]
6/13	46.2	[23.2, 70.9]
9/13	69.2	[42.4, 87.3]

As shown in [Table 6-4](#), there is limited power for a formal comparison of immunogenicity response rates between Group 7 (n=9) and Group 8 (n=9). For either 80% or 90% power, the sizes of differences that the trial is powered to detect are fairly large. These calculations use a Fisher exact 2-sided test with a type I error rate of 0.05.

Table 6-4 Power for comparison of response rates between 2 arms (n1 = 9, n2 = 9)

True response rate Arm 1 (%)	Minimum true response rate in Arm 2 in order to detect a difference	
	80% power	90% power
10	83	91
20	92	99
30	99	

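### Table 6-2: the safety confidence intervals for n = 10 and n = 44 are not the score intervals for the event counts they are labelled with

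*Protocol*

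**What the plan says.** Protocol section 6.2 describes safety precision in two ways: binomial detection probabilities (Table 6-1) and confidence intervals (Table 6-2). The title of Table 6-2 begins "Two-sided 95% confidence intervals based on observing a particular rate of safety endpoints for arms of size 3, 9, 10" and goes on to the combined arms of size 44. The text says that the table "shows the 2-sided 95% confidence intervals for the probability of an event based on a particular observed rate" and names the score test method. The rows cover 0, 1 and 2 events in 3, 9, 10 and 44 participants. These are the enrolled sizes: three per Part A group, all 44 combined, and for Part B "Actual Ns for Group 6, 7 and 8 were 10, 10 and 9 respectively".

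The text repeats the zero-event upper limits. For groups of 3, 9 and 10 the bound "in the total vaccinated population is 56.1% or 29.9% or 29.2%, respectively". For all 44 participants, "the 95% 2-sided upper confidence bound for this rate is 9.8" percent.

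SAP section 9 reprints the same table and the same text figures. Protocol section 6.2.1 uses the same method for Table 6-3, described as "Two-sided 95% CIs for the response rate based on observing a particular rate of responses in the vaccinees".

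**The concern.** Two features of Table 6-2 look wrong before any calculation. The 0/44 row has a lower limit of 0.1%, although no event has been observed and a score interval then starts at zero. The 2/10 row has an upper limit of 31.9%, below the 43.5% printed for 1/9 and far below the 54.7% printed for 2/9. Adding one participant cannot shorten the interval that much.

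Section 6.1 gives identifying safety concerns as the primary goal, and section 6 says the calculations were updated to actual enrolment. The n = 10 and n = 44 rows are therefore the real denominators for Groups 6 and 7 and for the whole trial. A reader who looks up two events in ten would conclude that true rates above 31.9% are excluded.

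**Working it through.** **Inputs.** Two-sided 95% level, so z = 1.96 and z² = 3.8415; score method; counts and sizes as labelled in Table 6-2 (Protocol section 6.2, repeated in SAP section 9).

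**Formula.** With p = x/n, the score (Wilson) limits are

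[ p + z²/(2n) ± z·√( p(1−p)/n + z²/(4n²) ) ] / ( 1 + z²/n )

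**Step 1: reproduce the plan's figures where possible.** For 2/9: p = 0.2222, centre term 0.4356, half-width term 0.3454, divisor 1.4268. This gives (0.4356 ∓ 0.3454)/1.4268 = 6.3% and 54.7%, as printed. The other five n = 3 and n = 9 rows also reproduce to rounding, as do all ten rows of Table 6-3. The formula is therefore the one the plan uses.

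**Step 2: apply it to the other six rows.** For 2/10: p = 0.2, centre term 0.3921, half-width term 0.3136, divisor 1.3841. This gives (0.3921 ∓ 0.3136)/1.3841 = 5.7% and 51.0%. With zero events the upper limit reduces to z²/(n + z²): 3.8415/13.8415 = 27.8% for n = 10 and 3.8415/47.8415 = 8.0% for n = 44.

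| Row | Printed (%) | Score interval at the labelled count (%) | Printed minus correct upper limit (points) |
|---|---|---|---|
| 0/10 | [0, 29.2] | [0, 27.8] | +1.4 |
| 1/10 | [0.1, 30.5] | [1.8, 40.4] | −9.9 |
| 2/10 | [0.2, 31.9] | [5.7, 51.0] | −19.1 |
| 0/44 | [0.1, 9.8] | [0, 8.0] | +1.8 |
| 1/44 | [0.3, 11.4] | [0.4, 11.8] | −0.4 |
| 2/44 | [0.6, 12.9] | [1.3, 15.1] | −2.2 |

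**Step 3: could another method explain the printed rows?** Clopper-Pearson, Agresti-Coull, Jeffreys, Wald and continuity-corrected Wilson were tried. None reproduces any of the six rows. For 2/10 their upper limits are 55.6%, 52.1%, 50.3%, 44.8% and 55.8%.

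**Step 4: what the printed rows do match.** Entering p = 0.01, 0.02 and 0.03 in place of 0/n, 1/n and 2/n gives:

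- n = 10: [0.02, 29.17], [0.09, 30.55], [0.20, 31.88]
- n = 44: [0.09, 9.77], [0.32, 11.39], [0.64, 12.91]

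All six agree with the printed rows to rounding.

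**Step 5: what the printed upper limits amount to.** At a correct score upper limit U, the statistic (x/n − U)/√(U(1−U)/n) has a lower tail of 2.5%. For 2/10 at U = 0.319 it is (0.2 − 0.319)/√(0.319 × 0.681/10) = −0.81, a tail of 21.0%. For the other printed limits the tails are 8.0% (1/10), 2.8% (1/44), 4.9% (2/44), 2.1% (0/10) and 1.4% (0/44). As an exact check, if the true rate were 31.9%, two or fewer events in ten would occur with probability 0.334.

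**The case against.** The arithmetic has no good answer; the case on the other side is about weight. Table 6-2 is offered only as another way to describe the design. Version 2.0 of the protocol was written after enrolment had closed at 44, so no sample size rests on it. Adverse events are reported as counts and percentages without formal comparison between arms (Protocol 6.5.3.2, SAP 10.4.2), the pause rules respond to individual events (Protocol 9.5), and the SAP's output list in section 11 names no table of adverse event confidence intervals. An interval reported for observed data would presumably be computed from those data, not read from this table. All of that stands, and it limits the consequence.

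The errors are also unequal. The 0/10 lower limit is correct, and the 1/44 row is off by only 0.1 and 0.4 points. Only 1/10 and 2/10 differ enough to change a reader's impression. The two bounds carried into the text err on the cautious side, so the prose does not make the products look safer than zero events would allow. This is also fair.

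It does not rescue the table. The rows are printed to 0.1 point under a named method, and the n = 3 and n = 9 rows meet that standard. Loss of content in reading the PDF is not an explanation, because the same figures stand in two documents and two of them are repeated in prose. Relabelling the rows as observed rates would not work either: 1%, 2% or 3% cannot be observed in ten people.

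**Conclusion.** The concern holds. All six n = 10 and n = 44 intervals are wrong for their labelled counts, in both documents. For one or two events the upper limits are too low, by 9.9 and 19.1 points at n = 10 and by 0.4 and 2.2 points at n = 44. The lower limits in those rows are also too low, so the printed intervals sit below where they should. For zero events the upper bounds are too high, by 1.4 points (n = 10) and 1.8 points (n = 44).

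The effect is confined to the stated safety precision; trial conduct and the planned analyses do not change. The conclusion assumes only that the score method named in the text was intended, which the rows that reproduce confirm. The explanation that 1%, 2% and 3% were entered as observed rates is an inference from the match, since the documents do not show the calculation. The finding does not depend on it.

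**What to change.** In Protocol section 6.2 and SAP section 9, replace the six rows of Table 6-2 with:

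- 0/10 [0, 27.8]
- 1/10 [1.8, 40.4]
- 2/10 [5.7, 51.0]
- 0/44 [0, 8.0]
- 1/44 [0.4, 11.8]
- 2/44 [1.3, 15.1]

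In the accompanying text, change the zero-event upper bounds from 29.2% to 27.8% (n = 10) and from 9.8% to 8.0% (n = 44). The n = 3 and n = 9 rows and Table 6-3 need no change. The cost is six table rows and two text figures in each document, with no operational consequence.
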